LGBTQ Cohort: Recruitment flyers (Recruitment Flyer for P&E.docx) will be distributed by school counselors to students in participating schools. Flyers will not be posted in any non-public area, rather they will be handed out to school clubs (i.e. Gay/Straight Alliance, Rainbow Club, etc) and to students directly by student counselors. Flyer contains information about the study and contact information for student counselors in their school. Students who endorse interest will have private and confidential meetings with their counselor regarding participating in this study. In week four of the school year, we will randomly select 12 names at each school from the LGBTQ+ youth identified via these recruitment methods to be invited to participate in the LGBTQ+ youth cohort portion of the study. These youth will be invited to a first P&E session, where they will be provided the link to the Proud & Empowered e-consent (or consent if they are 18+) form (P&E Assent Consent WUSTL 9.22.22.rtf), also hosted on RedCap and accessible via phone or school assigned tablet/computer.

Make Space Allies: To identify POL allies, P&E facilitator ([name]) will introduce the Make Space program, student advocacy and discuss the meaning of LGBTQ+ allies with our P&E students during session 4: Peers and Relationships. Students will then discuss allies whom they feel would benefit the Make Space project. Students will then begin nominating individuals who can serve as a popular opinion leader (POL) for the Make Space project. Students will select potential POL allies in session 6. School counselors/liaisons will then meet with these identified students and assess for the student's willingness to operate as an effective LGBTQ ally (e.g., willingness to provide visible support for SGM students), and students who are not interested, for any reason (related to topic or otherwise), will not be asked to participate. After screening each POL for interest in participation, Study Coordinator will then randomly select ten of the students identified to participate in the Make Space intervention portion of the study. Students who report interest and are chosen for participation will provide e-assent (or consent if they are 18+), similar to the process described for LGBTQ+ youth (on RedCap using phones or tablets). See "Make Space Intervention Procedures" below for more information on the Make Space assent/consent process.

Waiver of Parental Consent

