Proud & Empowered! Intervention: The proposed study is intended to rigorously test the efficacy of Proud & Empowered! (P&E) program in a large-scale RCT with 24 high schools across the Greater Los Angeles Area. Schools will be randomly assigned to an intervention or control condition. Schools assigned to the intervention condition will be further randomized to receive either just the P&E direct intervention or both P&E and Make Space. Detailed information on each program (Proud & Empowered! and Make Space) can be found in sections below. LGBTQ participants in the intervention schools will participate in P&E, whereas those attending control schools will complete only study survey measures during the study on the same timeline (all three time points) as the intervention schools.

LGBTQ Youth Procedures: For LGBTQ P&E participants, measures (information on measures can be found in the *Instrumentation* section below) will be obtained at three time points: the beginning of the P&E intervention (September), after the intervention period (November), and at the conclusion of the school year (May). LGBTQ+ student participant survey can be found in the attachments section as "Y2 P&E Survey.docx". LGBTQ+ youth participants will create a Unique ID, which the study team will use to link measures taken over time. Detailed information on recruitment of LGBTQ youth participants can be found in the *Recruitment* section above. School counselor will ensure there is a time and space available for each student to meet for a 45-minute intervention session once per week for 10 weeks. The study activities will occur at the school during school hours and the school counselor will ensure students can discreetly participate in the intervention sessions by either 1) grouping participating youth into the same homeroom/advisory period where the intervention will administered by Study Facilitator/Study Coordinator, or 2) providing students with a counseling slip, allowing them to miss a class to

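### School counselors help to form each school's recruitment pool, and nothing keeps the arm from them or from students, so pools can differ by arm and the draw of 12 does not correct that

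*Protocol*

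**What the plan says.** Protocol, Recruitment, LGBTQ Cohort. Counselors handle the recruitment material: "Recruitment flyers (Recruitment Flyer for P&E.docx) will be distributed by school counselors to students in participating schools". Flyers go to school clubs and also "to students directly by student counselors". The flyer names the counselor as the person to contact. Next comes a one-to-one conversation: "Students who endorse interest will have private and confidential meetings with their counselor regarding participating in this study". After that, "In week four of the school year, we will randomly select 12 names at each school", and the names come only from youth found by these means. For those drawn, "These youth will be invited to a first P&E session", where assent or consent is given. No separate wording is given for control schools.

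Protocol, Methods. The allocation sentence is "Schools will be randomly assigned to an intervention or control condition", followed by a second split: "Schools assigned to the intervention condition will be further randomized to receive either just the P&E direct intervention or both P&E and Make Space". No date is given for either step. Control youth complete surveys only. For the sessions, "School counselor will ensure there is a time and space available for each student". Surveys fall in September, November and May.

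Protocol, Data Analysis. A cluster-randomized repeated measures ANOVA is planned. No baseline covariate and no check of pool comparability is named.

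Combined protocol and SAP, Recruitment. The route differs. Students add their own names through a schoolwide survey, the Study Coordinator makes contact, and the draw is in week three. No concealment of the arm is stated there either.

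**The concern.** In a cluster trial, randomising schools balances the schools in expectation. It does not balance the individuals who are identified within them if those doing the identifying, or those volunteering, know the arm. Here the offer differs by arm: a ten-week support group in one, three surveys in the other. A counselor who knows that a group is coming has an ordinary, well-meant reason to mention it to a distressed or isolated student. A counselor at a survey-only school has less reason. Students' own interest can differ in the same way.

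The stake is the participant-level comparison on minority stress, depression, anxiety, PTSD and suicidality. If intervention pools hold more distressed youth, their scores start higher and tend to fall further with no intervention effect, which would look like benefit. If intervention pools hold less distressed youth, a real benefit would be partly hidden.

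**Working it through.** **1. What the documents settle.** I looked in both for the timing of randomisation relative to recruitment, concealment of the arm, masking of counselors, a common recruitment script, and a comparison of pools. None is stated. Neither document gives a power calculation, alpha or intraclass correlation (ICC), so there is no planned figure to reproduce.

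**2. What the draw does.** The cohort is at most 24 × 12 = 288 youth, or 144 per arm with 12 schools each. A random draw has the expected mean of its own pool. If intervention pools average b SD higher than control pools, the expected cohort difference is also b. The draw protects against choice within a pool, not against differences between pools.

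**3. Size under the planned analysis.** Assumptions: pool shift b = 0.1 to 0.3 SD; September-to-November correlation r = 0.5 to 0.7; no intervention effect; scores regress toward a common mean.

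- September difference = b
- November difference = r × b
- Difference in change = r × b − b = −b × (1 − r)

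| b (SD) | r = 0.5 | r = 0.7 |
|---|---|---|
| 0.1 | 0.1 × 0.5 = 0.05 | 0.1 × 0.3 = 0.03 |
| 0.2 | 0.2 × 0.5 = 0.10 | 0.2 × 0.3 = 0.06 |
| 0.3 | 0.3 × 0.5 = 0.15 | 0.3 × 0.3 = 0.09 |

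The range is 0.03 to 0.15 SD. If the shift is constant over time, the difference in change is b − b = 0.

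**4. A yardstick.** With 12 youth per school, no dropout and an assumed ICC of 0.01 to 0.10, the design effect is 1 + 11 × ICC = 1.11 to 2.10. The standard error at one time point is sqrt(2 × 1.11/144) = 0.124 to sqrt(2 × 2.10/144) = 0.171 SD. For change, multiply by sqrt(2 × (1 − r)), taking the same ICC for change scores. That factor is 1.00 at r = 0.5 and 0.775 at r = 0.7, so the standard errors are 0.124 to 0.171 and 0.096 to 0.132. The spurious difference therefore runs from 0.03/0.132 = 0.2 to 0.15/0.124 = 1.2 standard errors.

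**5. What adjustment for September does.** If scores regress as in step 3, adjustment leaves r × b − r × b = 0. If the shift is constant, it leaves b − r × b = b × (1 − r), the same 0.03 to 0.15 SD with the opposite sign. Neither analysis is safe under both patterns.

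**The case against.** The strongest reply is that the plan is silent, not wrong. It never says that schools are randomised before pools form, nor that counselors are told the arm. A reader might infer both, but no date or order is given. The one textual link between counselors and the arm is their scheduling role, and that does not require knowledge before the draw. This stands: the bias is possible, not shown.

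A reader might also take counselors to be gatekeepers who interview students and decide who receives a flyer. The text does not go that far. Clubs receive flyers too, students declare their own interest, eligibility rests on self-identification, and the conversations are described only as meetings. Where the Protocol wants counselors to assess students, as for Make Space Allies, it says so. What remains is influence through direct handing-out and an unscripted private meeting.

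The flyer's file name refers to P&E, but its content is in an attachment not included here, so one cannot say that it is not neutral. The start of flyer distribution is not given either.

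Nor does the Combined protocol and SAP show that the counselor route created the problem. Its schoolwide survey also states no concealment, and it presents the study as an intervention, so arm-dependent self-selection was possible there. The contrast is narrower: that route does not use counselors to build the pool.

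Finally, distress is measured in September, so much of any steering on distress would be visible. That is true and useful, but step 5 shows that visibility does not by itself give a correct adjustment.

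**Conclusion.** The point holds as an open route to identification bias. The Protocol, followed as written, permits pools that differ by arm, and the within-school draw cannot repair them. If schools are randomised after the pools close, the risk at this step is gone, but the plan would have to say so.

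The size is 0.03 to 0.15 SD in change from September to November. It rests wholly on the assumed shift, the assumed correlation and regression to a common mean, and it is zero for a constant shift. A reader might instead multiply shift by correlation and obtain 0.1 × 0.5 = 0.05 to 0.3 × 0.7 = 0.21 SD. That describes an unadjusted comparison in November alone, which is not the analysis planned.

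**What to change.** In the Protocol's Recruitment and Methods sections:

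- State that each school's condition, including the second split among intervention schools, is generated or released only after its pool is closed and its 12 names are drawn. Where feasible, wait until assent and the September survey are complete, because release at the draw still leaves both open to knowledge of the arm.
- Use one condition-neutral flyer, counselor script and first-session invitation in all 24 schools.
- Report pool size, number invited and number assenting, by school and arm.
- Prespecify adjustment for the September score. This supports concealment and does not replace it.
- Reconcile the recruitment routes in the two documents and say which one governs.

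The cost is protocol text and neutral materials. The small downside is that rooms and facilitators are confirmed later, although neutral time slots can be reserved at every school in advance. Waiting until after the September survey is harder, because that survey sits at the start of the P&E sessions; a common first session in both arms would be one way to do it.

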Efficacy of a Multi-level School Intervention for LGBTQ Youth NCT05541406 August 23, 2023

Study Protocol

Study Title: Efficacy of a Multi-level School Intervention for LGBTQ Youth

PI Name: [name]

Study Procedures

Background

Sexual and gender minority (SGM; e.g., lesbian, gay, bisexual, transgender, queer) adolescents experience victimization in schools at much higher rates than their peers. Studies, including meta-analyses, have found that gay and lesbian students are 8 to 10 times more likely to be victimized in school than heterosexuals, with rates even higher among transgender youth. Victimization comes from not only other students but also teachers and administrators. This bias-based victimization, part of what is commonly known as minority stress, has been associated with poor behavioral health outcomes for SGM adolescents. This includes disparate rates of depression, anxiety, self-harm, and suicidal ideation and attempt in sexual minority adolescents, with even stronger disparities found among gender minority adolescents. Even compared to similarly victimized non-SGM peers, victimized SGM adolescents report significantly higher rates of suicidality.

Studies also indicate that SGM victimization is more common in schools that lack protective policies and resources such as gender/sexuality alliances (GSAs), SGM-specific antibullying policies, teacher/staff training, and openly supportive allies. When schools lack SGM bullying policies, SGM students are more likely to report suicidality than peers in schools with these policies. We assert that any intervention for SGM youth must simultaneously (a) help SGM youth cope with minority stress and (b) work to reduce the likelihood of future victimization by addressing school-level factors. Thus, it is concerning that a recent review found there are no determinative studies, such as RCTs, of the efficacy of school-based interventions for SGM youth.

Objectives

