To fill this gap, we have developed a first-of-its-kind school-based intervention for SGM youth, Proud & Empowered! (P&E). The multi-level program was developed over the last 9 years through (a) psychometric, developmental, and acceptability studies funded by the NIH, foundations (Zumberge), and intramural sources; (b) a collaboration with three SGM youth dropin centers, more than 100 SGM youth, and a dozen academic and clinical experts; and (c) an exploratory study (R21MD013971) to assess the feasibility and preliminary efficacy of the intervention. Given encouraging findings, we now propose to employ a large-scale randomized controlled trial (RCT) with 24 schools in Los Angeles to establish program efficacy. At intervention sites (n = 12), after the 10-session small group portion of the intervention with SGM youth is completed, peer allies (who are identified through a popular opinion leader model) are invited to participate in 4-session leadership program focused on changing SGM-related school climate. This is followed by student-led implementation of environmental change strategies at the school level focused on key domains of school climate described by Thapa et al. (2013): safety, relationships, teaching and learning, and institutional environment. At the SGM student

level, analysis will focus on the hypothesized mechanism of change (minority stress) and key behavioral health outcomes (depression, anxiety, PTSD, suicidality, substance use).

Change in school climate will also be assessed qualitatively using content analysis and observational methods in the intervention and post-intervention years. Our specific aims are to:
1) Determine participant-level efficacy of the intervention in an RCT with 24 schools, 2)
Determine the schoolwide intervention effects on (a) reporting of minority stress and behavioral health outcomes among all SGM students and (b) perceptions of school climate (norms, attitudes, beliefs, bullying behaviors toward SGM youth, policies) among all students, and 3)
Examine factors that may affect intervention success (e.g., fidelity of implementation, barriers or facilitators to implementation, school or student characteristics) to prepare the intervention for future dissemination.

Participants

1. Inclusion Criteria:

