- a) P&E Intervention Participants will be eligible to participate if they: 1) are students at the selected schools, 2) self-identify as lesbian, gay, bisexual, transgender, or any other non-heterosexual/cisgender identity, 3) speak English, and 4) are able and willing to provide assent/consent.
- b) POL Allies/Make Space Participants will be eligible to participate if they: 1) are selected by P&E intervention participants as a popular opinion leader (i.e. students who others look up to and consider good leaders), 2) are willing to be an ally to the LGBTQ community, and 3) are able and willing to provide assent/consent.
- 2. Exclusion Criteria: not meeting the inclusion criteria above

3. Special Population:

- a) Minors: a waiver of parental permission for youth participation has been granted as there is concern that an IRB requirement of parental permission will put some sexual minority youth at risk regarding disclosure of their sexual orientation to their parents. This may then place these youth at risk for parental harassment, abuse, or expulsion from the parental home.
- b) Pregnant Women: There is no risk to pregnant individuals due to participation. Therefore, we will allow those who are pregnant to participate in the study.

4. Limitations:

- a) Although our feasibility trial had one school with 17 youth participating in the Proud groups, we found that this group was too large to manage effectively, and so we will limit the individual-level intervention group size to 12.
- b) Given that this is a Los Angeles-based study with a limited budget and that the majority of schools in the Greater Los Angeles Area are English speaking, we will be restricting enrollment those who speak English.

Recruitment

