Content analysis. Schools will provide the research team with access to current copies of the student handbook and internal policy documents that relate to LGBTQ students (including non-discrimination, curricular inclusion, name and pronoun policies, student data privacy protocols, gender-neutral facilities, bullying interventions, and suicide prevention policies). Schools will also provide the research team with recent copies of history, social science, and health education curriculum. The research team will conduct qualitative content analysis of provided materials, the result of which will compose part of a pre-Making Space intervention "policy scan" of the school. This process will be conducted in the year that the school participates and will be repeated in the same schools in the year following participation to allow for assessment of changes in policy over the intervention year.

Observational site visits. The research team ([name]) will conduct an on-site visit of the school during the intervention year and in the following year. To prepare for observational site visits, schools will be asked to provide a campus map, a list of student groups, and the meeting room for any LGBTQ-focused student group (such as Gender and Sexuality Alliances). During observational site visits, the research team members will walk around the school campus and take notes and photographs of campus facilities, such as classrooms and gender-specific facilities like restrooms and locker rooms. Notes and photographs will focus on the availability, acceptability, acceptability, and quality (AAAQ) of LGBTQ-specific or -relevant campus facilities, such as the classroom where an LGBTQ student group meets or the relative accessibility of gender-neutral restrooms vs gender-segregated restrooms. Photographs will only

be used as reference material to compare change from year to year and will not include any images of students, school staff, or school names or branding (i.e. the school mascot in the background). Photographs will be labeled in records using the date and time of the site visit, such that schools will not be associated with photographs by name.

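### No stratification or constraint is described for randomising the 24 schools, and no school covariate for the cohort analysis, although the Background names school features linked to outcomes

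*Protocol*

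**What the plan says.** Both documents plan a "large-scale RCT with 24 high schools across the Greater Los Angeles Area". The Objectives give 12 intervention schools ("At intervention sites (n = 12), after the 10-session small group portion"), which leaves 12 controls. The whole account of the first allocation, in Methods of both documents, is that "Schools will be randomly assigned to an intervention or control condition". The Protocol alone adds a second step: "Schools assigned to the intervention condition will be further randomized to receive either just the P&E direct intervention or both P&E and Make Space". Neither step comes with a stratum, a matching rule, a block or a balance constraint.

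The Participants section sets criteria for students only. Its one reference to schools is that participants "are students at the selected schools"; how schools are selected is not described.

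The Background of both documents states that "SGM victimization is more common in schools that lack protective policies and resources such as gender/sexuality alliances (GSAs", and its list continues with SGM-specific antibullying policies, staff training and visible allies. It separately links the absence of SGM bullying policies to suicidality.

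Under Data Analysis, both documents plan a cluster-randomized repeated measures ANOVA for the student cohort and name no school-level covariate. The combined document mentions school-level characteristics only for its schoolwide multilevel regressions, which the Protocol's Data Analysis section omits.

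**The concern.** With 24 clusters, simple randomisation cannot be relied on to balance a school-level factor, and the documents themselves identify factors associated with what the trial measures. GSA presence may matter in a second way. In the Protocol's Recruitment section the flyers are not posted; "rather they will be handed out to school clubs (i.e. Gay/Straight Alliance, Rainbow Club, etc) and to students directly by student counselors". A school with such a club may therefore yield a different set of 12 students from one without.

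If GSA schools fall unevenly, part of the observed arm difference reflects where they fell. Nothing described in the allocation or in the cohort analysis limits this. The information needed is already requested, since before the research team comes to the campus "schools will be asked to provide a campus map, a list of student groups, and the meeting room for any LGBTQ-focused student group". But that request belongs to a policy scan in the participation year. It is not tied to allocation or adjustment, and the text does not make clear that control schools are scanned.

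**Working it through.** The documents give no power calculation, intraclass correlation (ICC) or GSA prevalence, so there is no planned figure to reproduce. The only check is 24 = 12 + 12, which is consistent.

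**First allocation.** Let K of the 24 schools have a GSA (K is an assumption, so a range is shown). Under unrestricted 12 v 12 allocation the number X in the intervention arm is hypergeometric:

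P(X = x) = C(K, x) · C(24 − K, 12 − x) / C(24, 12), with C(24, 12) = 2,704,156.

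The gap between arms is |2X − K| schools. Four schools is 4/12 = 33 percentage points.

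For K = 12, a gap below four means X = 5, 6 or 7: (627,264 + 853,776 + 627,264) / 2,704,156 = 0.780. So P(gap ≥ 4) = 0.220.

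For K = 4, a gap of four means X = 0 or 4: 2 × 125,970 / 2,704,156 = 0.093.

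| GSA schools of 24 | P(gap ≥ 2) | P(gap ≥ 4) | P(gap ≥ 6) |
|---|---|---|---|
| 3 or fewer, 21 or more | – | 0 | 0 |
| 4 or 20 | 0.59 | 0.09 | 0 |
| 6 or 18 | 0.64 | 0.15 | 0.01 |
| 8 or 16 | 0.67 | 0.19 | 0.03 |
| 10 or 14 | 0.68 | 0.21 | 0.04 |
| 12 | 0.68 | 0.22 | 0.04 |

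With an odd K the gap is odd, so four or more means five or more. The same formula then gives 0.07 (K = 7 or 17) to 0.10 (K = 11 or 13), while a gap of three or more has probability 0.37 to 0.41.

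**Second allocation** (6 v 6 assumed; the split is not stated). With 6 of the 12 schools having a GSA, P(4 v 2 or worse) = 1 − C(6, 3)² / C(12, 6) = 1 − 400/924 = 0.57. With 4 or 8 it is 0.55, and with 3 or 9 it is 0.18. A 5 v 1 split or worse, with 6 GSA schools, has probability 0.08.

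**Size of a shift at a single time point.** Assume GSA and non-GSA schools differ by 0.2 to 0.3 SD on an outcome. An 8 v 4 split shifts the arm difference by (8/12 − 4/12) × 0.2 to 0.3 = 0.07 to 0.10 SD. The typical shift is smaller. For K = 12, Var(X) = 12 × 0.5 × 0.5 × 12/23 = 1.565, so the SD of the difference in proportions is 2 × √1.565 / 12 = 0.209, and the root-mean-square shift is 0.04 to 0.06 SD.

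For scale, with 12 students in each of 12 schools per arm and an assumed ICC of 0.01 to 0.10, the unadjusted SE of the arm difference is √(2 × (1 + 11 × ICC) / 144) = 0.12 to 0.17 SD.

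**With stratification.** Allocating 1:1 within GSA strata leaves a gap of 0 schools (even stratum) or 1 school (odd stratum). Allocating separately by enrolment year could add a little.

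**The case against.** The strongest reply is that randomisation already handles this. Chance imbalance has expectation zero, and an analysis that treats the school as the unit carries between-school variation, GSA-related variation included, in its standard error. That stands: the comparison is valid without stratification.

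Second, the cohort analysis has a September baseline. A stable GSA-related difference is present in September, November and May alike and largely drops out of the arm-by-time contrast. That also stands, so the 0.07 to 0.10 SD above is a single-time-point figure and should not be read as bias in the planned estimate. What baseline does not remove is any effect of GSA presence on change over the year or on response to the program. The documents offer no evidence for or against such an effect.

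Third, a reader might infer that any school may enter, that allocation is unstratified, and that GSAs drive victimization. The documents do not support these readings. They refer to selected high schools in Greater Los Angeles, they are silent on restriction and do not rule it out, and the Background reports associations only. Nor is a material imbalance likely: the 0.68 for a gap of two or more schools includes 7 v 5, one school away from balance.

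Fourth, recruitment does not depend on GSAs alone. The Protocol also uses counselors and other clubs, and the combined document recruits through a schoolwide survey. The second randomisation appears only in the Protocol, and its Data Analysis section states no comparison between the two intervention versions that an imbalance would distort.

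Finally, Aim 3 covers school characteristics, and the combined document's schoolwide models include them. Neither adjusts the cohort contrast.

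**Conclusion.** The concern holds in a limited form. Allocation and school eligibility are under-described, and neither the described design nor the cohort analysis uses a school factor that the documents themselves link to victimization. Under unrestricted allocation, a four-school gap in GSA presence has probability 0.15 to 0.22 for even numbers of GSA schools from 6 to 18, about half that or less for odd numbers in that range, and less again towards the extremes. The cost is chance imbalance and lost precision with few clusters; it does not invalidate the comparison. GSA prevalence, the ICC, the size of the GSA effect and the 6 v 6 split are all assumptions. If the sponsor already restricts the randomisation, what remains is to say so and to carry the factor into the analysis. This is an inexpensive improvement that should be made.

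**What to change.** 1. State the school eligibility criteria and the allocation method.
2. Record GSA presence (yes/no) for every school, control schools included, before allocation.
3. Stratify the school randomisation on GSA presence within enrolment year, and the second randomisation too where numbers allow. Keep to this one binary factor; adding bullying policy could leave strata too small (schools per year are not given).
4. Name GSA presence as a prespecified school-level covariate in the cohort analysis, including for schools already allocated.

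Possible wording: *Schools will be randomised 1:1 within strata of GSA presence in each enrolment year. The further randomisation of intervention schools will use the same strata where numbers allow. GSA presence will be a school-level covariate in the cohort analysis.*

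Cost: one item moved forward to school enrolment, a stratified allocation list, and about one school-level degree of freedom. No extra schools, students or staff are needed. The gain is small if nearly all or nearly no schools have a GSA.
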